1.1 Defining the Problem

Favorable outcomes in terms of quality of life, decreased symptom burden and freedom from atrial fibrillation (AF) are well established in patients with paroxysmal AF (PAF) who undergo pulmonary vein isolation (PVI). In more than 90 % of these patients electrical triggers and/or the electrical interplay between the left atrial body (LA) and the pulmonary veins are paramount for the initiation and maintenance of atrial fibrillation. Therefore efficient and durable PVI - when achieved - cures PAF in most patients.

Clinical experience and scientific studies however also agree that outcomes after PVI in patients with persistent atrial fibrillation (PeAF) are less favorable ¹ and PVI in these patients carries a much higher rate of recurrent AF related arrhythmias. This lower success rate has been attributed to the assumption that atria that persist fibrillating for prolonged time periods harbor more complex anatomical and physiological disease with myofibrillar remodeling and disarray, increased wall strain, fibrosis etc. This translates into a complex and insufficiently understood electrophysiological behavior of the atrial wall - e.g. extrapulmonary triggers and rotors^{2, 3}.

The relatively poor outcome after PVI alone in PeAF in comparison to PAF has been interpreted as owing to a shift in the relative pathophysiological importance of pulmonary vein triggers versus the above mentioned complex behavior of the LA - the "substrate" to maintain atrial fibrillation. Accordingly different approaches and concepts have been developed to modify or eradicate the extrapulmonary arrhythmogenic atrial substrate as an adjunct to pulmonary vein isolation. Different techniques include supplementary lines in both the left and the right atrium (RA), mapping and ablating presumptive rotating electrical wave fronts (rotors), targeting the ganglionic plexi in close proximity to the LA posterior wall ⁴ as well as specific targeting of complex fractionated electrograms (CFAE). In a comprehensive meta-analysis of available data on the relative efficacy of different ablation strategies in PeAF Wynn and coworkers recently found that there are no data available which clearly point to the best first-line ablation strategy in patients with PeAF ⁵. Their findings concur with another recent Cochrane analysis ⁶ which concluded, *first* that PVI remains the well documented baseline treatment, and *second* that supplementary lesions in the left atrium may increase the success rate in PeAF - however there is no scientific evidence to support one adjunctive ablation strategy added to PVI (e.g. PVI + roof line; PVI + CFAE ablations ; PVI + mitral isthmus line etc.) over the other. Current status is that ablating a limited number of supplementary lines in the left atrium is beneficial in PeAF. Which lesion set is better however still remains unsettled.

PeAF box feasibility ver 2.3

1.2 Demand and Opportunities

Due to the *demographic development* the population of patients with atrial fibrillation – both PAF and PeAF is expected to increase substantially over the next decades ⁷ and so is the need and expected demand for a safe evidence-based interventional treatment. In the area of AF ablation at least two important steps forward have been taken over the last couple of years: First *Technological development* such as reliable force sensing capabilities in the ablation catheters, precision and reliability of electro-anatomic mapping systems etc. Second, due to increased ablation activity the *operator experience* combined with optimization over time of *the entire EP-lab workflow* such as efficient and safe perioperative antithrombotic treatment have increased markedly.

Based on these developments ablation for **PAF** has become a relatively fast and safe procedure. PVI using wide area circumferential ablation (WACA) to obtain durable bidirectional block of electrical conduction between the pulmonary veins and the LA body is thus routinely achieved in most electrophysiology labs in Denmark. Success rates in terms of freedom from recurrence of symptoms or signs of AF, atrial tachycardia (AT) or atrial flutter (Afl) is - depending on the quality and quantity of post-procedure follow-up (FU) - currently perceived to be in the range of 60-70 % ¹ one year after one ablation for PAF with some late recurrences over the following years.

However, after one ablation for **PeAF** the one-year arrhythmia free rate is probably 30% ^{1, 8} although recent studies may point to arrhythmia free rates closer to 50 %. It must however be stressed that available data are heterogeneous and dependent on the follow-up scheme and the characteristics of the studied patient cohorts. For instance the duration of PeAF, the size of the LA, the presence of mitral valve disease, heart failure or other comorbidities contribute to the complexity of the single AF case and thus inversely to success rates after PVI.

It is widely accepted that success rates after PVI alone in PeAF are unsatisfactory. Until present time only relatively weak evidence point to positive effects of intervening with the electrical properties of the LA posterior wall (LAPW) by ablating one or two (thus isolating the LAPW) lines anchored to the isolated PVs.

Putative effects of "add on" LAPW isolation (LAPWI) may include:

- 1) The basic goal of isolating the pulmonary veins from the remaining LA is fortified at the posterior aspect where the box lesion will serve as a "second line of defense".
- 2) Posterior wall ablation may “inadvertently” damage or modify potentially pathophysiological important ganglionic plexi situated in close proximity to LAPW ^{9,10}.
- 3) Posterior wall fibrotic and potentially arrhythmogenic areas ¹¹ will be isolated from the remaining LA
- 4) Macro reentry tachycardias involving LAPW are hampered – given the lines remain intact.
- 5) Insufficient lines with gaps/slow conduction predispose to atrial flutters.

PeAF box feasibility ver 2.3

Thus: Effective LAPW-isolation added to PVI might carry significant benefits as first-line treatment in PeAF while in-effective LAPW isolation may worsen procedural outcomes. We therefore examined the currently available literature and ongoing studies which more or less directly address the putative antiarrhythmic effects of electrical isolation of LAPW. The findings are presented below.

2 Studies addressing adjunctive linear lesions in LA in PeAF.**2.1 Published studies**

1993 Cox et al ¹² published their 5 year outcomes in 65 patients (~50 % PeAF) whom they were able to follow up after the original surgical MAZE procedure which included several "cut and sew" lesions in both atria in order to conduct the sinus node impulse through a maze to the AV node. The core lesion in the LA was isolating the LAPW "en bloc" with the PVs although the concept of "PV triggers" was not known at that time. The procedure had a very high success rate but several serious complications including the need for permanent pacing and death.

First generation ablation technology (solid tip)

2003 Ernst et al. ¹³ studied the feasibility and effect of different lesion sets in the LA in 84 patients on freedom from AF. Electroanatomic mapping (EAM) using Carto® and solid-tip (non-cooled) ablation catheters were used. The different lesion sets were intended to combine PVI with other lesions and were often impossible to achieve as was the ability to achieve and maintain electrical conduction block with the technology used. One of the designs, the "A" type lesion set attempted to mimic the "core" line of the surgical Cox procedure. This design consist of one long continuous encircling line that isolates the paired PV ostia together with the posterior LA wall from the rest of the LA. In only one (of 20) patients this design led to complete (isolating) lines. This one patient was arrhythmia free at 3-years F-U. All other patients experienced early recurrences. The remaining lesion sets were all equally difficult to complete and inefficient. In retrospect the technology of those days was not sufficient to obtain durable isolating lines in the LA.

2004 Kottkamp et al. ¹⁴ followed patients one year after attempted WACA + roof line + mitral isthmus line in 100 AF patients (20 % with PeAF). They used solid tip ablation catheters and did not measure if PVI or electric conduction block of lines were achieved. At one year F-U 65 % of the PeAF pts - some on AAD had recurrence on 7 day ECG monitoring.

Second generation ablation technology (cooled tip)

2005 Fassini et al. ¹⁵ randomized 61 patients with PeAF to PVI with or without additional mitral isthmus block (PVI + MIB). At 18 months (50 % still on AAD) F-U only 36% in the PVI only group were recurrence free while 74% in the PVI + MI group were recurrence free.

2006 Willems et al. ¹⁶ randomized 62 patients with PeAF to PVI + CTI block or PVI + CTI block + roof line + MIB. They found that it was difficult to achieve electrical conduction block of both roof

PeAF box feasibility ver 2.3

line and mitral isthmus line. At long term F-U (70 weeks) only 20 % in the PVI + CTI group were in SR while 69 % of the patients with additional lines in the LA were in SR

2007 Sanders et al. ¹⁷ reported their results in 27 patients with "chronic" AF. Patients had a median continuous AF duration of 24 months at the time of the procedure and the atria were moderate-severely enlarged (AP diameter ~ 49 mm). Procedures started with patients in AF. First PVI, then CTI block and then LAPWI were performed. In five patients (19%) the AF terminated during LAPWI – either to SR or Afl. The patients had clinical follow up every three months for one year. Further F-U was outside protocol. 50 % of the patients developed atrial arrhythmias at an average of 10 months after the index procedure. Four of these patients were successfully re-ablated to SR off AAD while 1 patient achieved SR on AAD without further ablation. Using this strategy they achieved a 68% SR success rate at two years F-U.

2008 Gaita et al. ¹⁸ randomized 79 patients with PeAF in a 1:2 fashion to either PVI + CTI block (26 pts.) or PVI + Lines in LA + CTI block (53 pts.). Electrical conduction block to the pulmonary veins (PVI) was not formally tested and the persistence of the electrically blocking lines in the LA (roof line and mitral isthmus line) were not formally tested either. F-U continued for at least 3 years with 24 h Holter monitoring at intervals. At one year F-U after one procedure 27% of the PVI alone patients and 45 % in the PVI + lines experienced freedom from arrhythmia. After 3 years and additional ablations, if needed, 39 % and 75 % were free from AF.

2009 Tamborero et al. ¹⁹ studied 120 consecutive patients with AF (40% with PeAF) who underwent "baseline ablation" with PVI + MIB and randomized them to either additional roof line or roof line and inferior line that is: LAPW isolation. They used a single transseptal technique (no "lasso" catheter) and did not rigorously prove uni- or bidirectional PVI or electrical conduction block over the ablation lines. However in some of the patients offered LAPW isolation they demonstrated disappearance of signals in the LAPW box. At 10 months F-U the overall recurrence rate was 55% in both groups. No data were given pertaining to PeAF patients alone.

2010 Mikhaylov et al. ²⁰ Randomized 34 patients with longstanding PeAF to either a "baseline" lesion set consisting of PVI + roof line + MIB vs. "baseline" + septal line in LA anchored between the right superior pulmonary vein and the mitral annulus. PVI with electrical conduction block was shown using the lasso technique but conduction block over the other lines was not rigorously tested. At two year follow-up after one ablation the recurrence rate on AAD (Amiodarone or D-sotalol) was 60 % in both groups.

2011 Pak et al. ²¹ Investigated 200 patients with PeAF who in a non-randomized fashion were offered either PVI + roof line + MIB or PVI + roof + left atrial anterior wall line (LAAW). PVI and conduction block over the roof line were documented by pacing maneuvers in all patients. Ablation line conduction block was provable by differential pacing in 69% in the LAAW group whereas line durability was only shown in 32 % in the LLMI group. The one year AF free survival on AAD was 73% in the LAAW group compared to 63 % in the LLMI group.

PeAF box feasibility ver 2.3

2011 Estner et al.²² randomized 116 patients with PeAF to either PVI using WACA and addition of at least one but up to all three of the following lines: LA roof, LA anterior (RSPV to mitral valve) or CTI line in the right atrium (group 1) or ostial single vein PVI using spot lesions + elimination of all CFAE potentials in both atria (group 2). Cooled tip ablation. At one year F-U freedom from atrial tachyarrhythmia was 37 % in group 1 and 39% in group 2 after one single procedure.

2011 Chilukuri et al.²³ randomized 29 consecutive patients with AF (7 with PeAF) to either PVI or a "BOX" ablation much like Cox' original surgical "core line". They documented unidirectional electrical conduction block to the LAPW (but not the PVs *per se*) in the "BOX" group and the PVs in the PVI group. Follow-up was based on a portable leadless Omron® monitor with patients instructed to record 30 sec/day and during symptomatic episodes. At 10 months follow up the recurrence free survival was 25% in the "BOX" group and 15 % in the PVI group (P = 0,52). These were fairly poor results in both groups. Larger sample sizes, rigorous testing and documenting electrical conduction block over lines might have proven interesting.

2012 Lim et al.²⁴ randomized 220 AF patients (38% with PeAF) to receive either single ring ablation which attempts to isolate the pulmonary veins and LAPW in one continuous ring ablation (SRI) similar to the Cox core line OR a very wide WACA connected with a roof line (WAI). Both these groups were further randomized to MIB or not (2x2 factorial design). Most of the patients in all groups also had a CTI ablation. At two-year follow-up among the PeAF patients the AF free survival was 68 % in the SRI and 53 % in the WAI group (NS). Data on AF related (AF + Afl + AT) recurrence was not given for PeAF but overall was around 50% at 2 year follow-up. Attempted MIB was only successful in 54% of the patients randomized to that treatment. Sample size was obviously too small for comparison within the PeAF group.

2014 Saad and Slater²⁵ published a non-randomized series of 25 patients with both short- and longstanding PeAF lasting on average 11 months. At the initial procedure all patients had PVI + LAPWI + CTIB. Further, dormant conduction was induced with adenosine and ablated. AAD were continued for one month and ambulatory F-U was conducted at 1, 3, 6 and 12 months and 7 day Holter monitors were done when appropriate. On average F-U at 16 months 20 pts. (80%) were free from arrhythmia (two of these in AADs).

2014 Very recently Kim et al.²⁶ randomized 120 patients to PVI + several lines in the LA and RA (control) or the same lesion set as control + a lower posterior line thus leading to LAPW isolation. At 12 months F-U the AF recurrence rate was significantly lower in the LAPW group (17%) compared to control (37%).

Cool tip technology comparing "lines" and CFAE ablation

Dixit et al²⁷ randomized 156 patients with PeAF to 3 arms: 1. PVI + ablation of non-PV triggers identified using a stimulation protocol (standard approach); 2. Standard approach + empirical ablation at common non-PV AF trigger sites (mitral annulus, fossa ovalis, Eustachian ridge, crista ter-

PeAF box feasibility ver 2.3

minalis, and superior vena cava); or 3. Standard approach + ablation at sites of left atrial CFAE's. At one year follow up after one procedure on AAD's 49%, 58% and 29% of patients were free of atrial arrhythmias in arms 1, 2 and 3 respectively.

In the STAR AF II trial²⁸ a total of 549 PeAF patients were randomized in a 1:4:4 fashion in an international trial spanning four continents and 35 ablation centers to PVI, PVI + CFAE or PVI + Lines (roof + MIB). Surprisingly in the PVI only group freedom from AF and any AF related tachycardia after one procedure was 59 % (!) and 49 % respectively at 18 months follow-up. Another important finding was that in the "lines" group electrical block was only achieved in 74% of patients. Compared to PVI alone the outcomes at 18 months F-U tended to worsen in the PVI + lines and the PVI + CFAE groups (Freedom from AF 44% and 37 % respectively) !

Taken together these recent studies speak against the use of CFAE ablations and the proposed supplementary lesion sets in patients with PEAF.

2.2 Ongoing Studies (source: www.clinicaltrials.org)

A) *Outcome of atrial fibrillation ablation after permanent pulmonary vein antrum isolation with or without proven left atrial posterior wall isolation.*²⁹

A study initiated in August 2012 as collaboration between Texas Cardiac Arrhythmia Research Foundation, a center in Milan and two centers in China: Beijing and Wuhan. They started recruiting patients in 2013 for the study which randomizes patients with Atrial fibrillation PAF and "non-PAF" (short term and long term persistent) to either WACA or WACA + proven isolation of the left atrium posterior wall (LAPW). Recruitment appears to be multi-center. The technique of isolating the LAPW and schedule F-U is not depicted. A repeat procedure to prove and ensure, by further ablation if necessary, PVI and LAPW isolation will be mandatory three months after the index procedure. Estimated primary completion date was august 2014 and estimated publication is 2016. An estimated 400 patients will be recruited.

B) *Substrate Ablation and Remodeling in Non-paroxysmal Atrial Fibrillation (SMAAN-PAF)*³⁰

A study sponsored by The Liverpool Heart and Chest Hospital NHS foundation Trust. In a single center design 130 patients with "non-paroxysmal" atrial fibrillation are randomized and treated single blinded with PVI + amiodarone vs. PVI + amiodarone + additional lines (LA roof + mitral isthmus + CTI) Enrollment started 2011 and has stopped recruiting patients. Primary outcome measure is freedom from atrial fibrillation/ atrial tachycardia at 6 months following a single procedure.

2.3 Current status and ideas for further research**Status on linear lesions in PeAF**

As discussed there is presently no known "best practice" of supplementary lesions added to PVI in PeAF. Several studies were hampered by the ambition of investigating multiple hypotheses in one study resulting in comparison of small patient groups. Further, utilizing second generation technology with cool tip ablation the original idea from Cox' surgical "core line" with one single line encircling the PV's and the LAPW has been addressed in three relatively recent studies^{19, 23, 24} but the

PeAF box feasibility ver 2.3

effect in PeAF was impossible to assess due to technical and methodological problems. Recently the Star AF study appears to unambiguously negate any putative advantages of the alternative strategies other than PVI-only in PeAF used in that particular study.

However there is an unmet need to clarify if patients with PeAF will benefit from a combination of proper PVI with rigorous proof of bidirectional electrical conduction block AND electrical isolation of the LAPW with equally rigorous proof of durable bidirectional block. To our knowledge only one group worldwide currently conducts a randomized study to elucidate that problem ²⁹.

It is probably impossible to obtain 100% long term electrical conduction block in one procedure in all patients. However, in our EP-laboratory at Gentofte Hospital we frequently do add LAPWI to the lesion set on an empirical basis when, during the procedure, this option is perceived to be rational. With the current state of the art (not including SF catheters) we experience *first* that establishing proven LAPWI is relatively fast in most patients and *second* at re-do procedures the preliminary experience is that these BOX lesions tend to persist (i.e. still be blocked). Thus we believe that a combination of the latest technological developments and procedural techniques will allow a sufficiently high share of permanently isolated PVs and LAPWs during the index procedure to enable us to show putative advantages of that lesion set.

Important technological improvements and developments of procedures

- Third generation technological developments to optimize ablation lesions using contact force (CF) and *time-force-temperature-impedance* integration have become an integral part of AF- related procedures in our EP lab. Moreover, recently the *surround flow technology* (SF) offering even more efficient cooling than seen before has been integrated with the Smarttouch ® technology.
- Rigorously proving bidirectional electric block over all ablation lines to ensure PVI and LAPW isolation.
- Allowing proper intra-procedural waiting time supplied with adenosine testing for dormant conduction to detect and ablate early re-conduction.

Caveats - collateral damage

With larger lesion sets (such as PVI + LAPWI) and more efficient lesions - e.g. with SF Technology - the risk of damaging tissue surrounding the LA might increase. Most importantly the esophagus is notoriously prone to heat related lesions, ulcerations and eventually fatal fistulae. 2010 Halm et al. from Leipzig ³¹ published their data on 185 patients monitored with an esophageal temperature probe during LA ablation procedures. At esophagoscopy 1 day post procedure they found RFA related lesions in 14,5 % of the patients ranging from small superficial ulcer-like lesions to larger hemorrhagic lesions. Maximal esophageal temperature averaged 41,4 ° C in patients without lesions and 42,6 ° C in patients with lesions. No lesions were found if max temperature was ≤ 41 ° C. Later Knopp et al ³² found superficial thermal esophageal lesions in 11 % of 425 patients undergoing LA ablation using a cooled tip catheter in a steerable sheath. However, recently a Japanese group, per-

PeAF box feasibility ver 2.3

forming PVI for AF, allowed esophagus temperatures up to 42 ° C before pausing ablation. They found a range of lesions from erythema to frank ulcers in 25% of patients ³³.

Burning questions in ablation for PeAF - Aims of study:

There needs to be done a sufficiently powered randomized multicenter trial utilizing the latest technology to clarify if LAPWI as an adjunct to PVI is beneficial as a first procedure strategy in PeAF.

However, because of the substantial economical and logistical burden of such a study we suggest to first conduct a minor non-randomized, single center study. The aims of such as study is to clarify:

- 1) Utilizing SF-Smarttouch technology is it feasible to obtain PVI + LAPWI within a reasonable procedure- and fluoroscopy time ?
- 2) Is PVI + LAPWI with this potentially efficient technology safe ?
- 3) Is PVI + LAPWI durable ?
- 4) To uncover trends regarding the intermediate term effect on arrhythmia recurrence of this treatment ?

Depending on the outcomes of this study the obtained data will aid in the design of a randomized, study comparing the effects of PVI vs. PVI + LAPWI.

3 BOX - PeAF – feasibility study

3.1. Proposal of study

It is clinically and scientifically important to clarify if LAPW isolation as an adjunct to PVI in PeAF as a first line therapy is feasible and safe when utilizing the latest generation of ablation technology.

3.2 Primary aims

In patients who undergo first ablation for PeAF with WACA-PVI the addition of anchored lines connecting the zeniths of the superior pulmonary veins (roof) and the nadirs of the inferior pulmonary veins with proven isolation of the LA posterior wall (LAPW-isolation, LAPWI) is feasible, safe and durable.

Feasibility: **Descriptive:** In patients with PeAF and established WACA-PVI it is possible to establish complete electrical isolation (bidirectional conduction block) of the LAPW by ablating a superior and inferior line connecting the PVs within a reasonable prolongation / increase of procedure-, ablation- and fluoroscopy time.

Safety: **Hypothesis to be tested (see 3.4).** Guided by a temperature probe in the esophagus WACA-PVI+LAPWI can be achieved without increasing the incidence of inflammation/ injury to the esophageal epithelial lining as proven by endoscopy on the day after the procedure and compared to reported incidences of up to 30% in recently published studies.

Descriptive: WACA-PVI+LAPWI can be achieved without increasing the risk of pericardial effusion and tamponade as proven by post-procedure TTE.

Durability: **Descriptive:** At a *per protocol* interventional control procedure (independent of symptoms) 3 months after the index procedure a large proportion of LAPWs of PV's will remain durably isolated.

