3.7 Statistical Considerations

There will be no randomization or direct between-groups comparisons. Although this study is primarily exploratory and descriptive in nature we will formally test the hypothesis given in paragraph 3.4. Thus the sample size calculation of this study hinges on the need to demonstrate - with a reasonable power - that putative esophageal reactions to the WACA-PVI + LAPWI procedure do not exceed earlier findings after PVI alone.

PeAF box feasibility ver 2.3Calculation of sample size and power:

a) The outcome of esophagoscopy on day 1 after ablation in the LA is considered to be either positive (inflammation or other esophageal reaction is noted) or negative (no reaction). Therefore the probability distribution of outcomes of esophagoscopy will behave binomially.

b) Recent data indicate that esophageal reactions can be observed in the range of 10 % (proportion = 0.1) up to 30 % (proportion = 0.3) with the second generation ablation technology. We would be interested in showing that the proportion of esophageal reactions to WACA-PVI + LAPWI does not exceed proportions reported earlier (i.e. render probable that the proportion of any visible esophageal reaction to ablation is less than 0.3)

c) Setting as comparator that the underlying proportion (P) of patients subjected to this treatment that experience esophageal reactions is 0.3 or more AND assuming that the "true" proportion in our study is 0.1 then when:

- P =	0.3
- One-tailed α =	0.05
- "true" proportion =	0.1

- recruiting 23 patients will yield 80 % power to reject the (H_0) hypothesis that the proportion experiencing esophageal reactions is equal to or higher than the 0.3.

Based on these calculations we aim to recruit 23 patients for the study.

The above computations were aided by the software program (IBM/ SPSS - Sample power ® ver. 3.0.1)

Post - hoc analyses: Statistical analysis of input - and output data will be performed using IBM/SPSS ® ver. 22 using appropriate statistical methods.

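### The only formal safety test can show an oesophageal injury rate below 30%; it cannot show the absence of an increase over PVI alone that sections 3.2 and 3.7 attach to it

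*Combined protocol and SAP*

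**What the plan says.** - Section 3.2 (Safety) makes oesophageal injury the one hypothesis to be formally tested. The aim is worded as achieving the combined procedure with no rise in injury, "compared to reported incidences of up to 30% in recently published studies". No reference is attached to the 30%.
- Section 3.4 sets H0 as a proportion of at least 0.3 and H1 as a proportion below 0.3.
- Section 3.7 says the sample size rests on showing that reactions "do not exceed earlier findings after PVI alone". It gives a range of 10% to 30% for recent data, again without a reference, and treats not exceeding earlier proportions as equivalent to a proportion below 0.3. It also says there is no randomisation and no direct comparison between groups.
- The design inputs in 3.7 are: "Setting as comparator that the underlying proportion (P) of patients subjected to this treatment that experience esophageal reactions is 0.3 or more"; a true "proportion in our study is 0.1 then when"; a one-tailed α of 0.05; and the result that "recruiting 23 patients will yield 80 % power to reject the (H_0) hypothesis". Neither the test nor the rejection count is named.
- Section 2.3 (caveats on collateral damage) describes three endoscopy series. One reports lesions in 14.5% of 185 patients after left atrial ablation. A second "found superficial thermal esophageal lesions in 11 % of 425 patients undergoing LA ablation". The third is the only one described as PVI. It allowed oesophageal temperatures up to 42 °C before pausing, and of it the protocol says: "They found a range of lesions from erythema to frank ulcers in 25% of patients".
- Section 3.8 calls subclinical oesophageal inflammation the pivotal safety parameter, and section 2.3 says the results will help design a randomised comparison of PVI with PVI + LAPWI.

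**The concern.** The hypothesis that is tested and the conclusion that is drawn are different statements. With no PVI-alone group, the step from a rate below 0.30 to no increase over PVI alone holds only if 0.30 is a fair value for PVI alone. None of the three series described in section 2.3 reaches it. A rate that is clearly below 30% can still be well above 11% or 14.5%.

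Section 2.3 itself warns that larger and more efficient lesion sets might increase damage to surrounding tissue. If a rejection were reported in the words of 3.2 or 3.7, the planners of the randomised trial could take the added posterior-wall ablation as shown to carry no extra oesophageal risk. The data could not support that.

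**Working it through.** **Inputs.** From 3.7: p0 = 0.30, true p1 = 0.10, one-sided α = 0.05, n = 23. From 2.3: reference rates 0.11, 0.145 and 0.25.

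**1. The plan's own figure.** The arcsine approximation is n = [(z₀.₉₅ + z₀.₈₀) / (2·asin√p0 − 2·asin√p1)]².
- 2·asin√0.30 = 1.1593 and 2·asin√0.10 = 0.6435; the difference is 0.5158.
- n = [(1.645 + 0.842) / 0.5158]² = 23.2.
- Power at n = 23: Φ(0.5158·√23 − 1.645) = Φ(0.829) = 79.6%.

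The 23 patients and 80% power therefore reproduce.

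**2. Which rejection count this implies.** Exact binomial, X ~ Bin(23, p):

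| Reject if | Size at p = 0.30 | Power at p = 0.10 |
|---|---|---|
| X ≤ 2 | 0.0157 | 59.2% |
| X ≤ 3 | 0.0538 | 80.7% |

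The stated 80% matches X ≤ 3, whose exact size is slightly above 0.05. A strict exact test at 0.05 stops at X ≤ 2. The protocol does not say which applies.

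**3. What each result excludes.** The one-sided 95% exact (Clopper–Pearson) upper limit is the 0.95 quantile of Beta(x + 1, 23 − x). The exact p-value against a reference r is P(X ≤ x | r).

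| Positive | Observed | Upper limit | p vs 0.25 | p vs 0.145 | p vs 0.11 |
|---|---|---|---|---|---|
| 0 | 0% | 12.2% | 0.001 | 0.027 | 0.069 |
| 1 | 4.3% | 19.0% | 0.012 | 0.134 | 0.263 |
| 2 | 8.7% | 24.9% | 0.049 | 0.332 | 0.528 |
| 3 | 13.0% | 30.4% | 0.137 | 0.567 | 0.758 |

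Only zero events would exclude 14.5%, and no result in 23 patients excludes 11%. At the largest rejecting count, 25% is just excluded under the strict rule and is not excluded under the rule that gives 80% power.

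**4. Chance of rejecting H0 when the true rate is above cited rates.** At a true 20%, higher than two of the three series, P(X ≤ 2) = 13% and P(X ≤ 3) = 30%. At a true 25%, the figures are 5% and 14%.

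**5. Would a lower null solve it at n = 23?** With p0 = 0.25, P(X ≤ 2 | 0.25) = 0.049 and P(X ≤ 3 | 0.25) = 0.137, so the exact rule is X ≤ 2, with 59.2% power at a true 10%. By arcsine, 2·asin√0.25 = 1.0472, the difference is 0.4037, and power is Φ(0.4037·√23 − 1.645) = Φ(0.291) = 61%. Restoring 80% would take 38 patients (arcsine) or 45 (exact).

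**The case against.** The strongest defence is that the formal claim is already bounded. H1 is exactly a proportion below 0.3, section 3.7 explains not exceeding as meaning below 0.3, the study is called primarily exploratory and descriptive, and the PVI versus PVI + LAPWI question is left to a later randomised trial. This stands as a description of the test. It does not repair the no-increase wording of the aim in 3.2, or the phrase in 3.7 that names PVI alone as the comparator.

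Four stronger readings are tempting, and the documents do not support them.

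- *That 0.30 exceeds every rate in the protocol.* Sections 3.2 and 3.7 do assert rates up to 30%. The benchmark is the top of that range. It exceeds only the rates attributed to described series, and whether some other publication reports 30% cannot be settled from these documents.
- *That a rejection can never exclude a PVI rate.* Under a strict exact rule (at most 2 of 23), rejection also excludes 25% (p = 0.049), the rate in the one series described as PVI.
- *That a rejection leaves room for a doubling of the usual rate.* This needs the 11% and 14.5% series to be pooled as the reference: (0.145·185 + 0.11·425)/610 = 12.1%, against an upper limit of 24.9%. The trial counts any visible reaction. Those two series are described by superficial thermal lesions and by ulcer-like to haemorrhagic lesions, whereas the 25% series counts from erythema upwards and is the closer match. The pool leaves that series out.
- *That temperature practice alone disqualifies the 25% series.* The 14.5% series had mean maximum temperatures of 41.4 °C without lesions and 42.6 °C with them, so temperature does not separate the cohorts cleanly.

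**Conclusion.** The concern holds as a mismatch between the test and the conclusion. Rejecting H0 supports a rate below 30% and no more; it does not establish the absence of an increase, or parity with PVI alone. The one-sided upper limit at the boundary of rejection is 24.9% or 30.4%, depending on a cut-off the protocol leaves open. Either value is well above 11% and 14.5%.

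A reader might also infer that the sample size is wrong or that the null must be lowered. Neither follows: 23 patients reproduces on the plan's own inputs, and a null of 0.25 with 23 patients would make the 80% power statement untrue.

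The figures assume 23 evaluable endoscopies, independent binomial outcomes and, for power, a true rate of 10%.

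**What to change.** Keep H0 at 0.30 and the 23 patients.

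1. In 3.2 and 3.7, replace the no-increase wording and the comparison with earlier PVI-alone findings by a statement that the rate is below 30%.
2. Give the source or the justification for 30%.
3. In 3.7, name the test and the rejection count. If it is at most 3 of 23, state the exact size of 0.054. If it is at most 2 of 23, state the exact power of 59%.
4. Report the observed rate with its exact confidence interval beside 11%, 14.5% and 25%, noting that those cohorts differ in procedure, lesion definition and temperature practice.

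Do not move the null to 0.25 while keeping the 80% power statement.

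The cost is protocol wording only, with no added patients or data. The downside is a more modest safety claim.
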